7.2.3. Demographics, Disease Characteristics, and History

All demographics, baseline characteristics, and disease characteristics will be summarized using the mITT Set. Summary statistics will be presented by treatment group and overall. By-participant listings of these data will be provided.

7.2.3.1. Demographics and Baseline Characteristics

The following demographic variables will be summarized:

- Sex (female, male)
- Race (White, Black or African American, American Indian or Alaska Native, Asian, Native Hawaiian or other Pacific Islander, other)
- Ethnicity (Hispanic or Latino, not Hispanic or Latino)
- Age at Screening (years)
- Age categories (18 to < 40 years, 40 to < 65 years, \ge 65 years)
- Baseline weight (kilogram): Descriptive statistics (n, mean, median, SD, minimum, maximum) and frequency of participants in the following categories: 30 to < 40, 40 to < 60, 60 to < 100, ≥ 100 kg
- Baseline height (centimeter)
- Geographical region (EU, US, Japan, rest of the world)
- Time from TMA diagnosis to randomization
- TMA laboratory values (platelets, hemoglobin, LDH)

7.2.3.2. Disease Characteristics

The following characteristics will be summarized by treatment group and overall:

- Primary and additional trigger type
 - Autoimmune (lupus nephritis, SSc-TMA)
 - Infection
 - Solid organ transplant (eg, kidney, pancreas, liver, heart, small bowel)
 - Drugs
 - Malignant hypertension
- Organ dysfunction
 - Dialysis status during the Screening Period
 - eGFR
- PLASMIC score at Baseline (refer to Section 9.3.3)

7.2.3.3. Medical History and Baseline Physical Examination

Medical history will be classified by System Organ Class (SOC) and Preferred Term using the latest available version of standardized Medical Dictionary for Regulatory Activities (MedDRA) and will be reported by treatment group and overall for the Safety Set. Baseline physical examination information will be summarized by treatment group and overall for the Safety Set. By-participant listings of medical/surgical history and physical examinations will be presented.

7.2.4. Prior and Concomitant Medications/Procedures

Prior and concomitant medications (including vitamins and herbal preparations) and nonpharmacologic therapies and procedures will be summarized using the Safety Set. Prior medications or procedures are defined as medications or procedures taken within the 30 days prior to the first dose of study drug. Concomitant medications or procedures are defined as medications or procedures received by the participants on or after the first dose of study drug, including those started before the first dose of study drug and continued after the first dose of study drug.

Medications will be coded using the World Health Organization (WHO) Drug Dictionary version in use by Alexion at the time of the analysis, while nonpharmacologic therapies and procedures (any therapeutic intervention, such as surgery/biopsy or physical therapy) will be coded using MedDRA.

Medication summaries by treatment group (ie, number [%]) of participants using prior and concomitant medications will be presented by WHODrug Anatomical Therapeutic Chemical Level 3 and by WHO-Drug generic name. Procedures will be summarized similarly, but by MedDRA SOC and Preferred Term. Protocol-required vaccinations will be summarized similarly and will also be presented separately.

By-participant listings of these data will be provided separately.

7.3. Efficacy Analyses

The mITT Set is the primary analysis set for all efficacy analyses. The primary analysis will be repeated on the PPS as supplementary analyses.

7.3.1. Primary Analysis

The primary efficacy endpoint of the study is complete TMA response during the 26-week randomized Treatment Period.

Analysis of the primary endpoint will be conducted on the mITT Set based on randomized treatment groups using NRI for missing data handling. Point estimate and 95% confidence interval (CI) will be provided for the response rate for each treatment group. For participants who withdraw from the study, data up to the time of withdrawal will be used to assess complete TMA response.

Additionally, the primary efficacy endpoint will be analyzed based on the PPS.

7.3.1.1. Subgroup Analysis

Summaries of the primary efficacy endpoint will be presented by trigger type (including the primary trigger).

7.3.2. Secondary Analyses

All secondary analyses will be performed on the mITT Set.

For time-to-event endpoints, Kaplan-Meier cumulative distribution curves will be generated for each treatment group. A corresponding summary table will present by treatment group the cumulative distribution function estimate, the number of participants at risk, the number of participants responding, and the number of participants censored at each post-Baseline time point. The table will also present the first quartile, median, and third quartile, along with the corresponding 2-sided 95% CI, of time to response.

The binary additional secondary endpoints will be summarized by randomized treatment group by calculating the point estimate and 2-sided 95% CI for the response rate, based on exact confidence limits using the Clopper-Pearson method (Clopper, 1934). NRI will be used to handle missing data.

For continuous additional secondary endpoints, descriptive statistics, including the number of participants, mean, SD, minimum, median, and maximum, will be provided based on observed data.

For participants who require dialysis, change from Baseline in dialysis requirements will be summarized. An analysis will present the number and proportion of participants who require dialysis over time. A 2-sided 95% CI for the proportion will be provided. A participant will be considered as not requiring dialysis at a specific post-Baseline time point if they have been dialysis free for at least 14 days prior to that time point.

7.4. Interim Analysis

No interim analysis would be performed due to early termination of the study.

7.5. Exploratory Analyses

7.5.1. Biomarkers

Planned analyses on exploratory biomarkers will be detailed in a separate, exploratory biomarker SAP. Exploratory biomarker assessments will be reported in a separate biomarker report.

7.5.2. Patient-Reported Outcomes

Quality of life will be analyzed for EQ-5D-5L and KDQOL-36.

For EQ-5D-5L, a visual analogue scale (VAS) and the health state index score using US time trade-off (TTO) will be calculated (based on Section 9.3.13) and summarized at Baseline and each scheduled post-Baseline time point using descriptive statistics for continuous variables for the observed value as well as the change from Baseline.

For KDQOL-36, Short-Form Health Survey 12 Item (SF-12, item 1-12), burden of kidney disease (item 13-16), symptoms/problems of kidney disease (item 17-28b), and effects of kidney disease scales on daily like (item 29-36) as subscales will be calculated separately by taking the sum of the component items. Descriptive statistics as well as the change from Baseline by visits will be presented separately for each subscale.

7.5.3. Health Resource Utilization

Hospitalizations will be summarized in a table presenting the number and proportion of participants requiring hospitalization, as well as the number of hospitalizations, the duration, the reason for hospitalization, and the hospitalization setting (intensive care unit or general ward).

Outpatient medical encounters will be summarized by presenting the number and proportion of participants requiring physician or emergency-room visits and the underlying reason.

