### 2.2. Background

Thrombotic microangiopathy is a rare, life-threatening disease often caused by complement activation that results in endothelial damage. In some patients, complement-mediated TMA may result from a trigger that injures the endothelium, such as post-partum, malignant hypertension (sometimes termed hypertensive emergency), infection, transplant (solid organ or bone marrow), autoimmune disease, and certain drugs (Aigner, 2019; Go, 2016; Goodship, 2017; Park, 2018). Many patients present in critical condition, require management in an intensive care unit, and often need dialysis. Once multiorgan dysfunction develops, patients have a poor prognosis (Le Clech, 2019).

Two complement C5 inhibitors, ravulizumab and eculizumab, are approved for the treatment of patients with aHUS, a type of complement-mediated TMA. There are currently no approved therapies for the broader complement-mediated TMA population. Treatment typically consists of corticosteroids and/or therapeutic plasma exchange (TPE) or plasma infusion. The underlying trigger may also be treated, along with other supportive measures (eg, transfusion, dialysis), as appropriate. While TPE/plasma infusion will improve hematologic parameters in complement-mediated TMA, neither corticosteroids nor TPE/plasma infusion will address the underlying complement dysregulation and the TMA process is likely to persist (Azoulay, 2017; Kavanagh, 2006; Laurence, 2013). Removal of the trigger and supportive care are sometimes sufficient to reverse TMA symptoms; however, in patients with severe renal manifestations, outcomes are not greatly improved after removing/treating the trigger and providing supportive care.

In patients with aHUS, ravulizumab achieved immediate, complete, and sustained inhibition of terminal complement and improved renal function (Rondeau, 2020). It is hypothesized that

ravulizumab will be similarly effective in the treatment of complement-mediated TMA at the approved aHUS dosing regimen.

A detailed description of the chemistry, pharmacology, efficacy, and safety of ravulizumab is provided in the Investigator's Brochure (IB).

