To assess PK/PD of ravulizumab in participants with TMA	
Serum ravulizumab concentrations over time
 
Absolute values, change from baseline, and percentage change from baseline in serum free C5 concentrations over time

Objectives	Endpoints
	Absolute values, change from baseline, and percentage change from baseline in serum total C5 concentrations over time
To characterize the potential for immunogenicity of ravulizumab in participants with TMA	Incidence and titers of ADAs over time
Safety	
To characterize the safety profile of ravulizumab in participants with TMA	Incidence of AEs and SAEs by Week 26 and Week 52 Incidence of MACEs (Section 8.4.5) by Week 26 and Week 52 Changes from baseline in vital signs and laboratory parameters at scheduled assessments
Exploratory	
To assess improvement in extrarenal manifestations	Extrarenal manifestations by Week 26 and Week 52
To assess impact of treatment on resolution of hemolysis	RBC transfusions by Week 26 and Week 52
To assess improvement in patient-reported QoL outcomes	Change in patient-reported outcomes as measured by EQ-5D-5L and KDQOL-36
To assess biomarkers and autoantibodies in participants with TMA	Exploratory biomarkers will be assessed in blood and urine for change from baseline and may include but are not limited to, markers of vascular damage, renal injury and complement dysregulation (eg, sC5b-9, factor Ba).
To assess complement pathway genetic mutations in participants with TMA associated with a trigger	Incidence of complement dysregulation-related mutations
To assess health resource utilization during the study	Number and duration of hospitalizations (including stays in intensive care unit, if applicable) Number of outpatient visits (including physician and emergency room visits)
To assess impact on overall survival	Overall survival by Week 26 and Week 52

a Key secondary endpoints. The primary and key secondary efficacy analyses will use a hierarchical stepdown closed-testing procedure as described in Section 9.4.1.3.

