5.3. Exploratory Endpoints

The exploratory endpoints of the study are as follows:

- Exploratory biomarkers will be assessed in blood and urine for change from Baseline and may include, but are not limited to, markers of vascular damage, renal injury, and complement dysregulation (eg, soluble terminal complement complex, factor Ba). Exploratory biomarker assessments will be detailed in a separate, exploratory biomarker SAP.
- Change in patient-reported outcomes as measured by EuroQol 5-Dimension 5-Level (EQ-5D-5L) and Kidney Disease Quality of Life instrument[™]-36 items (KDQOL-36) at scheduled visits
- 3. Incidence of complement dysregulation-related mutations
- 4. Health resource utilization by Week 26 and Week 52 including:
 - Number, underlying reason, and duration of hospitalizations (including stays in intensive care unit, if applicable)
 - Number of outpatient medical encounters (including physician or emergency room visits)
- 5. Overall survival by Week 26 and Week 52

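### The SAP defines outpatient use as a number of encounters by Week 26 and Week 52, but its planned summary counts only participants with any visit, so the defined count is never reported

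*SAP*

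**What the plan says.** **Endpoint.** SAP 5.3 item 4 opens with "Health resource utilization by Week 26 and Week 52 including" and lists two components. The outpatient one is "Number of outpatient medical encounters (including physician or emergency room visits"). The inpatient one is "Number, underlying reason, and duration of hospitalizations (including stays in intensive care unit, if applicable"). Protocol Table 4 also states outpatient use as a count, "Number of outpatient visits (including physician and emergency room visits"), but without week cuts. Protocol 8.11.2 again lists the number of outpatient encounters and their reason, and leaves out encounters that the protocol itself requires.

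**Analysis.** SAP 7.5.3 plans for outpatient use: "Outpatient medical encounters will be summarized by presenting the number and proportion of participants requiring physician or emergency-room visits and the underlying reason". For hospital use, its preceding sentence goes further. Besides the participants hospitalized, it plans summaries "as well as the number of hospitalizations, the duration, the reason for hospitalization, and the hospitalization setting (intensive care unit or general ward"). Neither sentence repeats the Week 26 and Week 52 cuts or names a starting day.

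**Setting.** Protocol Table 1 collects medical resource utilization at Screening (Day -14 to Day -1) and continuously afterwards. SAP 4 reports 16 participants enrolled and the decision to end the study once the last participant in treatment finishes the 26-week Treatment Period. SAP 4.2 drops all inferential comparison of the arms.

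**The concern.** An endpoint defined as a count should be summarised as a count. Here the quantity named in SAP 5.3 has no output in SAP 7.5.3. The planned table reduces each participant to yes or no, which discards frequency, the thing a resource-use endpoint is meant to describe. If most participants have at least one visit, the table says little about either arm.

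Two gaps sit beside this. First, follow-up is unequal. Participants randomized later can leave before Week 52 because the study stops when the last one completes Week 26. An outpatient summary with no time cut and no follow-up time would then mix different observation periods. Second, hospital use has no stated start. The protocol says of this disease that "Many patients present in critical condition, require management in an intensive care unit, and often need dialysis". Some participants may therefore already be in hospital at Day 1, and the SAP does not say how such an admission enters the number or the duration.

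**Working it through.** Neither document states a visit rate, admission rate or expected result for resource use, so there is no planned figure to reproduce. The check has three parts.

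**1. Endpoint against analysis**

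| Component | Defined in SAP 5.3 item 4 | Summarised in SAP 7.5.3 |
|---|---|---|
| Hospitalizations | number, reason, duration, including ICU stays | participants (n, %), number, duration, reason, setting |
| Outpatient encounters | number | participants with any visit (n, %), reason |
| Time points | Week 26 and Week 52 | not repeated |

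The hospitalization row matches and the outpatient row does not. The omission cannot easily be read as implied, because the hospitalization sentence lists participants and events as separate items and the outpatient sentence lists only participants.

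**2. What an any-visit proportion retains**

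Let m be the mean number of encounters per participant. All values of m are assumptions.

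- Poisson counts: P(any visit) = 1 - exp(-m)
- More dispersed counts (negative binomial, shape 1): P(any visit) = 1 - 1/(1 + m)

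| Assumed m | Poisson | Negative binomial, shape 1 |
|---|---|---|
| 1 | 63.2% | 50.0% |
| 2 | 86.5% | 66.7% |
| 3 | 95.0% | 75.0% |
| 6 | 99.8% | 85.7% |

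A twofold difference in encounters would then appear as follows:

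- 6 against 3, Poisson: 99.75% - 95.02% = 4.7 points
- 6 against 3, negative binomial: 85.7% - 75.0% = 10.7 points
- 2 against 1, Poisson: 86.47% - 63.21% = 23.3 points
- 2 against 1, negative binomial: 66.7% - 50.0% = 16.7 points

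So the same doubling shows as anything from about 5 to about 23 points, depending on the level and spread of the counts. A table of proportions does not let the reader recover the counts.

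At the actual size, 16 participants at 1:1 is about 8 per arm. If every participant in one arm had 1 visit and every participant in the other had 12 (a made-up extreme), the totals would be 8 × 1 = 8 and 8 × 12 = 96. The planned table would show 8/8 in both arms.

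**3. Time cuts and start point**

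SAP 7.7.2.4 reports MACE through Day 183 and Day 365 with patient-years of follow-up. SAP 7.7.2 separates pretreatment from treatment-emergent adverse events, and SAP 7.2.4 separates prior from concomitant medication. SAP 7.5.3 has no equivalent of either device, although collection begins up to 14 days before Day 1.

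**The case against.** The strongest reply is that little depends on this. The endpoint is exploratory, the study ended early with 16 participants, and SAP 4.2 removes treatment comparisons. With about 8 per arm, even 8/8 has an exact 95% lower limit of 0.025^(1/8) = 63%, so no summary of outpatient use will be precise. That stands, and it keeps the point minor. It does not remove the mismatch, because descriptive output is all this endpoint will have.

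It can also be said that the week cuts are already in the endpoint definition and need not be repeated, and that tabulating reasons visit by visit would recover the counts. The first is a fair reading. The second is possible, but SAP 7.5.3 does not say whether reasons are tabulated per visit or per participant.

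Three stronger readings are tempting, and the documents support none of them.

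- *A reader might infer that the proportions will be near 100% in both arms.* No visit or admission rate is given, the protocol speaks only of many patients in critical condition, and protocol-mandated encounters are excluded. A ceiling is one scenario among those in the table.
- *A reader might infer that the admission under way at Day 1 is counted as an outcome.* No rule says so. Protocol Table 1 is a collection schedule, and the SAP is silent.
- *A reader might infer that resource use cannot show any difference.* For hospital use, number, duration, reason and setting are all planned, and these can differ even if every participant is admitted once.

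**Conclusion.** The point holds for the outpatient endpoint. SAP 5.3 defines a count by Week 26 and Week 52, and SAP 7.5.3 contains no summary of it. This rests on the text alone and needs no assumption.

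The size of the information loss cannot be fixed from the documents. Under assumed means of 1 to 6 encounters and two count distributions, the any-visit proportion runs from 50% to 99.8%, so the loss could be modest or nearly complete. Priority is low: an exploratory, descriptive endpoint in a terminated study of 16 participants, with no bearing on the primary endpoint or on safety.

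The missing start point for hospitalizations is a lesser matter of unstated detail, not a demonstrated error.

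**What to change.** In SAP 7.5.3:

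1. Add, by treatment group, the number of outpatient encounters per participant (mean, SD, median, range) by Week 26 and by Week 52, with physician and emergency-room visits shown separately. Keep the existing any-visit proportion and reasons.
2. Show follow-up time next to each summary, since not everyone will be observed to Week 52.
3. As a clarification, state that the number and duration of hospitalizations are counted from Day 1, and identify separately any admission ongoing on that day.

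The cost is a few lines of SAP text and some programming. Protocol 8.11.2 already calls for the number of outpatient encounters and for the number and duration of hospitalizations, so no new procedure is needed. The documents do not say whether visit dates, visit type, and admission and discharge dates are captured. The sponsor should confirm this, because the week cuts, the split by visit type and the Day 1 rule depend on them. If the dates are missing, report the total count and note the limitation.

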7.6. Pharmacokinetic and Pharmacodynamic Analyses

Individual PK/PD data will be collected for all participants. PK/PD analyses will be performed on the PK/PD Analysis Set.

Serum ravulizumab concentration will be summarized over time with descriptive statistics, including the number of observations, arithmetic mean, SD, median, minimum, maximum, coefficient of variation, geometric mean, and geometric coefficient of variation.

The PD effects of ravulizumab will be evaluated by assessing the observed values, changes and percentage changes from Baseline in serum free and total C5 concentrations over time, as appropriate. Summaries will present descriptive statistics at each sampling time, as appropriate.

7.7. Safety Analyses

All safety analyses will be conducted on the Safety Set and based on the actual treatment received. All safety data will be provided by treatment group, in participant listings. AEs will be coded in MedDRA and presented by MedDRA SOC and Preferred Term. No formal hypothesis testing is planned. Safety data will be presented separately for the 26-week randomized Treatment Period and Post-Treatment Follow-up Period.

7.7.1. Study Treatment Duration and Treatment Compliance

Study treatment duration, numbers of infusions received, and treatment compliance will be summarized for the Safety Set. Study treatment duration will be calculated (in weeks) starting from the first infusion of study drug.

Treatment compliance will be calculated as a percentage based on the number of infusions received out of the number of infusions expected.

7.7.2. Adverse Events

The following definitions will be used for AEs:

- Pretreatment AEs: Any AE that starts after providing informed consent/assent, but before randomization or before the start of the first infusion of study drug.
- Treatment-emergent adverse event (TEAE): Any AE that starts between the first infusion of study drug and up to 8 months after the last infusion of study drug.
- Treatment-emergent serious adverse event (TESAE): A TEAE that is serious.

The incidence of TEAEs, TEAEs leading to withdrawal from the study, TEAEs leading to study treatment discontinuation, drug-related TEAEs, TEAEs during study drug administration, and SAEs will be summarized by treatment group. All AEs will be coded using MedDRA version 23 or higher and will be summarized by SOC and Preferred Term overall, severity, and relationship to treatment. Participants having multiple AEs within a category (eg, overall, SOC, Preferred Term) will be counted once in that category. For severity/relationship tables, the participant's highest grade/most related event within a category will be counted. Percentages will be based on the number of treated participants in the Safety Set within a treatment group and overall. Tables will be sorted by descending frequency of SOC and by descending frequency of Preferred Term within an SOC.

Detailed by-participant listings of pretreatment AEs, TEAEs, SAEs, related TEAEs, TEAEs during study drug administration, TEAEs leading to withdrawal from the study, and TEAEs leading to study treatment discontinuation will be provided.

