This was a Phase 3, randomized, double-blind, placebo-controlled study of ravulizumab in addition to best supportive care (BSC) in adult participants (\geq 18 years of age) with thrombotic microangiopathy (TMA) following a defined trigger. All participants had severe acute kidney injury and a diagnosis of TMA based on protocol-defined criteria (ie, thrombocytopenia, microangiopathic hemolytic anemia, and elevated lactate dehydrogenase [LDH]), which was associated with at least 1 trigger, such as autoimmune, infection, solid organ transplant, drugs, or malignant hypertension, occurring \leq 14 days prior to randomization.

The study consisted of an up to 2-week Screening Period, a 26-week randomized Treatment Period, and a 26-week Post-treatment Follow-up Period. Thus, the total treatment duration was 26 weeks, and the total study duration was up to 54 weeks.

Participants were screened for eligibility for up to 2 weeks during the Screening Period. Approximately 100 adult participants were planned to be randomized in a 1:1 ratio to receive either ravulizumab or placebo. Randomization was stratified by baseline dialysis status and by primary trigger type.

During the 26-week Treatment Period, all participants received a weight-based loading dose of ravulizumab or placebo on Day 1, followed by weight-based maintenance doses of ravulizumab or placebo on Day 15 and then once every 8 weeks (q8w) thereafter. All participants received BSC throughout the study.

During the 26-week Post-treatment Follow-up Period, participants continued to receive BSC at the discretion of the Investigator and will be monitored for safety, TMA response, and clinical events of interest.

The end of the study was defined as the last participant's last visit in the Post-treatment Follow-up Period.

Enrollment in the study was closed, and the decision to terminate the study when the last participant in treatment has completed the 26-week Treatment Period was made on 24 Oct 2022.

Disclosure Statement: This was a parallel group treatment study with 2 arms that was participant, Investigator, and outcomes assessor blinded.

Number of Participants: It was planned that approximately 100 participants would be enrolled in the study. A total of 16 participants were enrolled in the study.

Intervention Groups and Duration:

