5.5. Safety Endpoints

The safety and tolerability endpoints of the study are as follows:

- 1. Incidence of adverse events (AEs) and serious adverse events (SAEs) by Week 26 and Week 52
- 2. Incidence of major adverse cardiovascular events (MACEs) by Week 26 and Week 52
- 3. Changes from Baseline in vital signs and laboratory parameters at scheduled assessments

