6.4. Safety Set

The Safety Set will include all participants who receive at least 1 dose of study drug. Participants will be analyzed according to the study treatment they actually received. For a participant to be analyzed according to the treatment they actually received and not according to the randomization schedule, they would have to receive that treatment for all their study drug exposure visits. All safety analyses will be performed on the Safety Set.

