7.7.2.1. Overall Summary of Adverse Events

An overall summary of AEs and SAEs will be presented. The number of events (n) and number of participants with events (n, %) will be shown for the following event subcategories:

- Any TEAE
- Any TESAE
- TEAEs leading to withdrawal from the study
- TEAEs leading to study treatment discontinuation
- Study drug-related TEAEs
- TEAEs during study drug administration

Additionally, the number and percentage of participants who died during the study will be presented. AEs and SAEs by SOC and Preferred Term. The number of AEs and the number and

percentage of participants with events will be presented by SOC and Preferred Term. Participants are counted once in each SOC and Preferred Term. Percentages will be based on the total number of treated participants in the treatment group. SAEs will be summarized similarly.

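### Follow-up Period AE percentages use all treated participants as denominator although early termination leaves some with little or no follow-up, so they understate incidence among those observed

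*SAP*

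**What the plan says.** SAP 7.7 splits the safety output by period: "Safety data will be presented separately for the 26-week randomized Treatment Period and Post-Treatment Follow-up Period". SAP 7.7.2 then gives the denominator for AE tables: "Percentages will be based on the number of treated participants in the Safety Set within a treatment group and overall". SAP 7.7.2.1 repeats it for the tables by System Organ Class and Preferred Term: "Percentages will be based on the total number of treated participants in the treatment group". Entry to the Safety Set (SAP 6.4) needs one dose only: "The Safety Set will include all participants who receive at least 1 dose of study drug". Neither document sets a separate denominator, a censoring rule or person-time for AEs in follow-up.

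SAP 5.5 keeps as an endpoint "Incidence of adverse events (AEs) and serious adverse events (SAEs) by Week 26 and Week 52". The design in SAP Section 4 has "a 26-week Post-treatment Follow-up Period", but the same section reports that "the decision to terminate the study when the last participant in treatment has completed the 26-week Treatment Period was made on 24 Oct 2022". SAP 4.1 runs the only remaining analysis at that point. Patient-years are planned for MACE alone (SAP 7.7.2.4), through Day 183 and through Day 365.

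**The concern.** A percentage for a later period is read as the risk among people observed in that period. Here some treated participants will not have been observed in it, or only briefly, because the study was stopped. Dividing by everyone treated counts them as followed and free of events.

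The period matters for safety. Treatment-emergent AEs run to 8 months after the last infusion (SAP 7.7.2). The last scheduled dose is Day 127 (Protocol Table 7), so for a fully dosed participant that window covers the whole planned follow-up. No treatment comparison will be tested (SAP 4.2), so these descriptive percentages are the main summary of post-treatment safety.

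**Working it through.** The plan states no figure on this point, so there is none to reproduce.

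**Who lacks follow-up**

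- Termination: if the last participant in treatment completes Week 26, the study ends there and that person has essentially no follow-up. A participant randomized w weeks earlier (w < 26) has about w of the planned 26 weeks.
- Withdrawal from the study during treatment: Protocol 8.4.1 collects AEs to 8 weeks after the last dose. The latest scheduled dose is Day 127, and 127 + 56 = Day 183, so collection stops at about the start of follow-up. The number of such withdrawals is not given.
- Stopping study drug alone does not remove follow-up: Protocol 7.1 asks that these participants continue to Week 52.

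**Effect of the denominator**

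Let N be the number treated, m the number with no follow-up and x the number with an event in follow-up. The SAP reports x/N; among those who entered follow-up the figure is x/(N − m). The relative shortfall is 1 − (N − m)/N = m/N, so for any x > 0 and m ≥ 1 the SAP figure is the lower one.

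SAP Section 4 gives 16 enrolled. It does not give the split by arm, the number treated or the number entering follow-up. Assuming all 16 were treated, with x = 3 for illustration:

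| m (hypothetical) | Entered | SAP rule | Entrants only | Relative shortfall |
|---|---|---|---|---|
| 1 | 15 | 3/16 = 18.8% | 3/15 = 20.0% | 1/16 = 6.3% |
| 2 | 14 | 18.8% | 3/14 = 21.4% | 2/16 = 12.5% |
| 4 | 12 | 18.8% | 3/12 = 25.0% | 4/16 = 25.0% |

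**Effect of partial follow-up**

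Under a constant hazard (assumption), a true 26-week incidence p appears as 1 − (1 − p)^f when a fraction f of the period is observed. At f = 0.5, p = 20% appears as 1 − 0.80^0.5 = 10.6%, and p = 40% as 1 − 0.60^0.5 = 22.5%. This shortfall remains even when only entrants are counted.

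**How many are truncated**

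Randomization dates are not given. If entry were even over T weeks, a share 26/T would have less than full follow-up. The span from the original protocol date (16 Dec 2020, Protocol 10.15) to the termination decision (24 Oct 2022) is 677 days, or 96.7 weeks. That gives 26/96.7 = 26.9%, about 4 of 16. With T = 52 it is 50%. These are people with shortened follow-up, most of whom did enter the period, so they are not values of m.

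**Week 52**

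For cumulative incidence from Day 1 every treated participant was at risk at the start, so all treated is a proper denominator. The shortfall comes from observation ending early. Eight months is about 243 days, so the treatment-emergent window for a fully dosed participant closes near 127 + 243 = Day 370. Someone cut off at Day 183 has been observed for 56 of those 243 days, or 23% of the time after the last infusion.

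**The case against.** The strongest reply is that the share of all treated participants with an observed event is a well-defined and conventional summary. An entrants-only percentage conditions on surviving and staying in the study, and it still treats someone cut off after a week as fully followed. This stands in part: changing the denominator alone is not enough, and person-time is needed to handle truncation.

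It is also fair that the follow-up denominator is read from a general rule, since no sentence states the N for follow-up tables. But no exception is made either, and a programmer following SAP 7.7.2 would use all treated.

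The practical harm is limited. Only 16 participants were enrolled, event and participant counts accompany the percentages, AEs and deaths are listed by participant, and disposition is reported by arm. That lets a careful reader see the problem, but it does not correct the tables.

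Three stronger readings are tempting and not supported:

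- A reader might infer that no cumulative Week 52 AE table will exist. SAP 7.7 requires separate presentation but does not exclude a cumulative one, and the treatment-emergent window already spans Day 1 to Week 52 for a fully dosed participant.
- A reader might infer that the Week 52 endpoint has the wrong denominator. It does not; its weakness is truncated observation.
- A reader might infer very large errors, such as 25% in place of 40% or 50% (2 of 8 against 2 of 5 or 2 of 4). That needs 3 or 4 of an assumed 8 per arm never to enter follow-up, whereas the documents imply only one such participant overall.

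**Conclusion.** The point holds for Follow-up Period AE percentages. As written, SAP 7.7, 7.7.2 and 7.7.2.1 together understate incidence among those observed, provided at least one event occurs in follow-up and the last participant completes treatment or someone else never enters the period. The size is not computable from the documents. The denominator effect is m/N, about 6% in relative terms for the one participant the termination rule implies (1 of 16, all treated) and 25% if there were 4. Partial follow-up adds an unknown amount.

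Treatment Period percentages and the MACE patient-year rates are not affected. A difference between arms would arise only if truncation differed by arm. That could happen by chance with 16 participants, but nothing in the documents shows it. This is an inexpensive improvement worth making, not a flaw that undermines the safety analysis.

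**What to change.** In SAP 7.7.2 and 7.7.2.1:

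- Base Follow-up Period percentages on participants who entered that period, and define entry (for example, any AE observation after the Week 26 visit). Show counts and the all-treated N alongside, because the entrants-only figure conditions on remaining in the study.
- Report by arm the patient-years observed and the participants with events (or events) per 100 patient-years, both for the Follow-up Period and for Day 1 to Week 52. SAP 7.7.2.4 already does this for MACE to Day 183 and Day 365. The person-time part is what deals with partial follow-up and serves the Week 52 endpoint in SAP 5.5.

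The cost is one extra denominator flag and a few table rows, with no new data. Follow-up percentages will look less favourable, and with 16 participants the rates will be imprecise.
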